2.3.2 Benefits from Study Participation

Participants vaccinated with the 2021–2022 NH formulation of Fluzone High-Dose Quadrivalent vaccine may be protected against those strains included in the vaccine and may be less likely to develop complications during the influenza season. However, in the context of this study, the influenza vaccine will be injected 4 to 6 months ahead of the NH influenza season which may lessen the influenza vaccine's potential protective effect during the influenza season.

Participants receiving Moderna COVID-19 Vaccine may be protected against SARS-CoV-2 infection and may be less likely to develop COVID-19 illness (26).

In addition, Fluzone High-Dose Quadrivalent vaccine will be offered to participants randomized to Group 3 at the conclusion of their participation to the Active Phase. Group 3 participants will be reminded that the Advisory Committee on Immunization Practices (ACIP) recommends yearly influenza vaccination, especially in high risk groups such as adults \geq 50 years of age. This vaccination will be entirely voluntary, free of charge to participants, and will take place after all V02 study procedures have been completed. This vaccination will be offered as part of routine medical care and no additional data related to this vaccination will be collected. It is to be noted that vaccination with Fluzone High-Dose Quadrivalent vaccine offered to Group 3 participants at V02 will not be considered by the Sponsor as meeting exclusion criterion #14 (See [Section 5.2](#)).

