1.3 Schedule of Activities (SoA)

The study Schedule of Activities (SoA) for all 3 treatment groups is presented in [Table 1.1](#).

Visit procedures are detailed in the Operating Guidelines.

Table 1.1: Schedule of activities

**Phase II Study, 2 Visits, 2 Telephone Contacts, either 1 or 2 Vaccination, 2 Blood Samples,
180 Days' Duration Per Participant**

Visit (V) / Telephone Contact (TC)	Collection of information in the CRF	V01	TC1	V02	TC2 6-Month Safety Follow-up
Study timelines (days [D])		D01	D08	D22	D181
Time interval (days)			V01 + 7 days	V01 + 21 days	V01 + 180 days
Time windows (days)			[+2 days]	[+3 days]	[+14 days]
Visit procedures:					
Informed consent	X	X			
Inclusion/exclusion criteria	X	X			
Collection of demographic data	X	X			
Collection of medical history *	X Significant Medical History	X			
History of seasonal influenza and COVID-19 vaccination	X	X			
Physical examination †		X			
Pre-vaccination temperature		X			
Randomization / Allocation of participant number	X	X			
Blood samples (BL) for Ab assays (20 mL) ‡	X	BL0001		BL0002	
Vaccination (VAC)	X	VAC1 (all groups) VAC2 (Group 1)			
Immediate surveillance (30 min)	X	X			
Diary card (DC) provided		DC1§			
DC reviewed			DC1**		
DC collected				DC1††	
Memory Aid (MA) provided				X	
MA reviewed					X
Collection of solicited injection site and systemic reactions	X	Up to 7 days after vaccination			
Collection of unsolicited AEs	X	Up to 21 days after vaccination			
Collection of concomitant medications	X Reportable concomitant medication	X		X	
Telephone contact			X		X##
Collection of SAEs, AESIs, and MAAEs §§	X	To be reported at any time during the study			
End of Active Phase participation record ***	X			X	
End of 6-month safety follow-up ***					X

Abbreviations: Ab, antibody; AE, adverse event; AESI, adverse event of special interest; BL, blood sample (#); CRF, case report form; D, Day; DC, diary card; SAE, serious adverse event; ; MAAE, medically-attended adverse event; SARS-CoV-2, severe acute respiratory syndrome coronavirus 2; V, Visit; VAC, Vaccination; MA, Memory Aid.

- * Including history of COVID-19 infection.
- † Targeted physical examination will be performed at V01. If needed, targeted physical examination based on medical history and Investigator's discretion might be performed at the other vaccination visit(s).

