5.4 Screen Failures

Screen failures are defined as participants who consent to participate in the clinical study but are not subsequently randomly assigned to study intervention. Screening information is recorded in the source documents.

Individuals who do not meet the criteria for participation in this study (screen failure) cannot be rescreened.

5.5 Criteria for Temporarily Delaying Enrollment, Randomization, Administration of Study Intervention, or Blood Draws

Not applicable.

6 Study Interventions and Concomitant Therapy

Study intervention is defined as any investigational intervention(s), marketed product(s), placebo, or medical device(s) intended to be administered to a study participant according to the study protocol.

Note: Vaccines or products administered outside of study protocol are not considered as study interventions and are reported in the CRF as reportable medications (see [Section 6.8](#)). Study procedures (eg, blood sampling) are also not considered as study interventions.

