6.8 Concomitant Therapy

Reportable medications include medications that may affect the interpretation of safety data (eg, an antipyretic or analgesic that could have reduced the intensity or frequency of an adverse event) or may interfere with the development or measurement of the immune response (eg, the use of immune-suppressors, immune-modulators, or some antibiotics that can affect certain bioassays). Some medications such as steroids can affect both the evaluation of the safety and the immune response to a vaccine.

This may include medications of interest that were started prior to the day of vaccination, and even stopped prior to enrollment if there is a reasonable possibility that they may have an impact on safety and / or immune assessment during study participation.

The following reportable medications are defined:

- medications impacting or that may have an impact on the evaluation of the safety (eg, antipyretics, analgesics, and non-steroidal anti-inflammatory drugs [NSAIDs], systemic steroids/corticosteroids)

Note: Topical analgesics should NOT be applied at the injection site of study intervention; however, if they are applied inadvertently, they should be recorded.

- medications impacting or that may have an impact on the immune response (eg, other vaccines, blood products, antibiotic classes that may interfere with bioassays used by Sanofi Pasteur laboratory or other testing laboratories, systemic steroids/corticosteroids, immune-suppressors, immune-modulators with immunosuppressive properties, anti-proliferative drugs such as DNA synthesis inhibitors)
- medications impacting or that may have an impact on both the safety and the immune response (eg, systemic steroids/corticosteroids)

Reportable medications will be collected in the CRF until the end of the solicited and unsolicited follow-up period.

Dosage and administration route, homeopathic medication, topical and inhaled steroids, as well as topical, ophthalmic, and ear treatments will not be recorded (except topical analgesics applied at the injection site of study intervention).

Medications given in response to an AE will be captured in the “Action Taken” section of the AE CRF only. No details will be recorded in the concomitant medication Form of the CRF unless the medication(s) received belongs to one of the pre-listed categories. Medications will be coded.

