8.3.1 Time Period and Frequency for Collecting AE and SAE Information

Immediate Post-vaccination Observation Period

Participants will be kept under observation for 30 minutes after vaccination to ensure their safety. The post-vaccination observation should be documented in the source document.

Reactogenicity

Solicited injection site reactions will be collected from the day of vaccination (D01) until 7 days after vaccination (D08).

Solicited systemic reactions will be collected from the day of vaccination (D01) until 7 days after vaccination (D08).

The solicited injection site reactions and systemic reactions that are pre-listed in the diary cards and CRF, together with the intensity scales, are presented in [Appendix 10.2.5.1.1](#).

Unsolicited Non-serious Adverse Events

Unsolicited non-serious adverse events will be collected from the day of vaccination (D01) until 21 days after vaccination (D22).

The intensity grading scale for unsolicited non-serious adverse events is presented in [Appendix 10.2.5.1.2](#).

Medically Attended Adverse Events (MAAEs)

MAAEs will be collected from D01 to D181.

Adverse Events of Special Interest (AESIs)

AESIs will be collected from D01 to D181.

See [Section 8.3.6](#) for the list of AESIs.

SAEs

Information on SAEs will be collected and assessed throughout the study, from the time of vaccination (D01) until 6 months after vaccination (D181). However, before the first study intervention administration, only SAEs related to study procedures are to be collected in the case report form (CRF).

All SAEs will be recorded and reported to the Sponsor or designee immediately and under no circumstance should this exceed 24 hours, as indicated in [Appendix 10.2](#). The investigator will submit any updated SAE data to the Sponsor within 24 hours of it being available.

Investigators are not obligated to actively seek information on AEs or SAEs after conclusion of the study participation. However, if the investigator learns of any SAE, including a death, at any time after a participant has been discharged from the study, and he/she considers the event to be reasonably related to the study intervention or study participation, the investigator must promptly notify the Sponsor.

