9.3 Analysis Sets

For the purposes of analysis, the following analysis sets are defined:

Participant Analysis Set	Description
Randomized	All participants that have a randomization number
Safety Analysis Set (SafAS)	Participants who have received the study vaccine(s). All participants will have their safety analyzed according to the vaccine they actually received and study intervention group. Safety data recorded for a vaccine received out of the protocol design will be excluded from the analysis (and listed separately).
Immunogenicity analysis set (IAS)	Subset of randomized participants who received at least 1 dose of study vaccine. Participants will be analyzed according to the vaccine they actually received and study intervention group.

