An unsolicited AE is an observed AE that does not fulfill the conditions of solicited reactions, ie, pre-listed in the CRF in terms of diagnosis and onset window post-vaccination. For example, varicella or a solicited term such as headache starting after the solicited observation period (eg, headache starting on Day 10 post-vaccination in the case where headache occurring between the day of vaccination and the next 7 days is pre-listed in the protocol and CRF as a solicited reaction).

An unsolicited AR is an unsolicited AE that is considered related to an IMP.

Unsolicited AEs includes both serious (SAEs) and non-serious unsolicited AEs.

All unsolicited AEs occurring at and around the IMP injection/administration site are to be considered by default as related to the IMP administered at that site and are therefore referred as unsolicited injection/administration site ARs.

All unsolicited AEs which are not at and around the IMP injection/administration site, are referred as systemic unsolicited AE. For each unsolicited systemic AE, the investigator assesses the relationship to the IMP. Systemic AEs assessed as related to IMP are referred as systemic ARs.

Adverse Event of Special Interest (AESI):

An adverse event of special interest (serious or non-serious) is one of scientific and medical concern specific to the Sponsor's study intervention or program, for which ongoing monitoring and rapid communication by the investigator to the Sponsor can be appropriate. Such an event might warrant further investigation in order to characterize and understand it. Depending on the nature of the event, rapid communication by the study Sponsor to other parties (eg, regulators) might also be warranted.

Medically Attended AE (MAAE)

An MAAE is a new onset or a worsening of a condition that prompts the participant or participant's parent/legally acceptable representative to seek unplanned medical advice at a physician's office or Emergency Department. Physician contact made over the phone or by e-mail will be considered a physician office visit for the purpose of MAAE collection. This includes medical advice seeking during the study visit or routine medical care. This definition excludes pediatric check-ups, follow-up visits of chronic conditions with an onset prior to entry in the study, and solicited reactions.

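### Six-month safety tables: D22 falls in two reporting windows, and Group 3's rows can mix Moderna alone with Moderna followed by Fluzone HD in a proportion the plan does not secure

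*Protocol*

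**What the plan says.** **The offer.** Protocol 2.3.2 offers Fluzone HD to Group 3 participants when they finish the Active Phase: "This vaccination will be entirely voluntary, free of charge to participants, and will take place after all V02 study procedures have been completed". It adds: "This vaccination will be offered as part of routine medical care and no additional data related to this vaccination will be collected".

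**Recording of other vaccines.** The opening note of Protocol Section 6 says: "Vaccines or products administered outside of study protocol are not considered as study interventions and are reported in the CRF as reportable medications". Section 6.8 then limits the period: "Reportable medications will be collected in the CRF until the end of the solicited and unsolicited follow-up period". In the Schedule of Activities (Table 1.1), the row "Collection of concomitant medications" is marked at V01 and V02 only.

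**Analysis.** SAP 3.4.1 takes the vaccine and study group from the labels of the D01 injections. SAP 4.2.1.2.3 assigns unsolicited AEs when one vaccine was given and when two were given concomitantly; it has no rule for a second vaccine given later. The safety analysis set carries an exclusion (Protocol 9.3, repeated in SAP 3.3): "Safety data recorded for a vaccine received out of the protocol design will be excluded from the analysis (and listed separately").

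**Windows.** SAP 4.2.1.2.4 defines within 21 days as onset from D1 to D22, or missing. SAP 4.2.1.2.6 to 4.2.1.2.8 report MAAEs, SAEs and AESIs within 21 days, from D22 to 180 days, and within 180 days.

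**Scope.** The safety objective is limited to the 21 days after injection, but the SAE, AESI and MAAE endpoints listed under it run to 6 months (Protocol Table 3.1, SAP Table 2.1). SAP 3.4.2 centres the co-administration safety assessment on Groups 1 and 3.

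**The concern.** There are two separate problems in the six-month tables.

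1. **D22 is counted twice.** This affects all three groups. An event starting on D22 meets both window definitions, so early and late event counts can add to more than the 180-day count.
2. **Group 3 may have two exposures.** After V02, an accepter has had Moderna and then Fluzone HD but is still tabulated under the D01 label. Without a count of recipients, a reader cannot tell how far the Group 3 row describes Moderna alone. That matters because Group 3 is the comparator the SAP singles out for co-administration safety.

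**Working it through.** **1. Day labels.** SAP 4.2.1.2.4 sets onset day = start date − vaccination date + 1. So 21 days after vaccination is 21 + 1 = D22, and 180 days after is 180 + 1 = D181. Both agree with the Schedule of Activities.

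**2. Window overlap.**
- D1 to D22: 22 days.
- D22 to D181: 181 − 22 + 1 = 160 days.
- Sum: 22 + 160 = 182, against 181 days in D1 to D181. The one repeated day is D22.
- With a D23 start: 181 − 23 + 1 = 159 days, and 22 + 159 = 181, with no overlap and no gap.

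One event on D22 gives 1 early, 1 late and 1 overall, so event counts fail to sum. Participant counts need not sum under either rule: someone with one early and one late event is in both period rows and once in the overall row.

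**3. Is the post-V02 dose recorded?**
- The Section 6 note points to yes, as a reportable medication.
- Section 6.8 ends that collection with the unsolicited period, which closes at D22 (Protocol 8.3.1).
- The last scheduled collection is V02, and the dose follows all V02 procedures.
- Section 2.3.2, the only text specific to this dose, says no additional data.

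The passages do not settle it, and nothing guarantees that a count of recipients will exist. The safety-set exclusion does not close the gap. It cannot be applied without a record of receipt, and the plan does not say whether a dose the protocol itself offers is out of the protocol design.

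**4. Extent of mixing.** Share of an accepter's 180 days after the dose = (181 − day of dose)/180. Assumption: the dose is given on the day of V02, which has a +3-day window (D22 to D25). A later dose lowers the share.
- V02 on D22: 159/180 = 88.3%.
- V02 on D25: 156/180 = 86.7%.

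Multiplying by uptake, which is not stated:

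| Assumed uptake | Group 3 180-day follow-up after Fluzone HD |
|---|---|
| 0% | 0% |
| 25% | 21.7% to 22.1% |
| 50% | 43.3% to 44.2% |
| 75% | 65.0% to 66.2% |
| 100% | 86.7% to 88.3% |

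This measures mixing, not bias.

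**5. What could move in the tables.**
- *Guillain-Barré syndrome.* Protocol Table 2.1 puts any excess at slightly more than 1 per 1,000,000 vaccinated. For 100 participants: 100 × 0.000001 = about 0.0001 cases. The documents give no such figure for the other AESIs.
- *MAAEs.* Protocol 10.2.1 says: "This definition excludes pediatric check-ups, follow-up visits of chronic conditions with an onset prior to entry in the study, and solicited reactions". Solicited collection stops at D08 (Protocol 8.3.1). A listed reaction in the week after a D01 injection is therefore not an MAAE. The same reaction after the post-V02 dose could be one if it prompts unplanned medical advice, provided the safety-set exclusion does not remove it.
- *Scale.* Protocol 9.2 expects 100 × (1 − 0.05) = 95 evaluable per group. Each participant added moves the Group 3 percentage by 1/100 = 1.0 point, or 1/95 = 1.05 points. The planned exact 95% interval at n = 100, for assumed rates, is:
  - 5%: 1.6% to 11.3%, 9.6 points wide before rounding the limits.
  - 10%: 4.9% to 17.6%, 12.7 points wide.
  - 20%: 12.7% to 29.2%, 16.5 points wide.

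**The case against.** The case for leaving the plan alone has several sound parts.

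- **The objective is framed to 21 days.** This stands. The SAP's reason for focusing on Groups 1 and 3 is reactogenicity, which is collected only to D08. A reader might infer that the main co-administration safety comparison is compromised. The documents do not support that: the dose comes after all V02 procedures, so solicited reactions and D22 immunogenicity are untouched, and the 21-day tables are touched only by events on D22 itself. The six-month events are still listed endpoints and should be interpretable.
- **Events are judged one by one.** This stands in part. Investigators weigh alternative causes, including concomitant therapy, and the sponsor also assesses SAEs and non-serious AESIs (Protocol 10.2.3). The later dose can be considered for each event, but that does not supply the number of recipients.
- **Splitting Group 3 by the post-V02 dose does not isolate Moderna alone.** This stands. E14 concerns vaccines only up to 4 weeks after injection, and medication collection ends early in every group. A Group 3 participant who declines may be vaccinated elsewhere, and later vaccines in Groups 1 and 2 are not captured either.
- **The offer is disclosed and followed regulatory review (Protocol 10.5).** Agreed. The offer is not in question, and tables by D01 vaccine are legitimate if labelled.

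**Conclusion.** Both parts hold, as a minor point.

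The D22 overlap is certain from the text: one day of 181 is in two windows, in every group. Only event counts are affected in principle. It would be wrong to say that a D23 start makes participant rows add up.

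The mixing in Group 3's six-month rows is possible at any proportion from none to nearly all of the time after V02. The 86.7% to 88.3% per accepter rests on a same-day dose, and the group-level figures also rest on assumed uptake. A reader might infer that Group 3's late rates are biased, or that its MAAE rate must be inflated. Neither follows: no uptake or event rate is given, and whether the exclusion rule applies is unsettled. The likely effect is small and mainly on MAAEs, but its size and direction cannot be derived from the documents. There is no hypothesis test, so no error rate or power figure changes.

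**What to change.** 1. **SAP 4.2.1.2.6 to 4.2.1.2.8:** start the later window at D23.
2. **Protocol 2.3.2, Section 6 note and 6.8:** leave the offer unchanged, and reconcile the three passages so that receipt (yes/no) and date of the post-V02 Fluzone HD dose are recorded in the CRF. At the existing D181 call, ask all groups about any other influenza or COVID-19 vaccine received since V02.
3. **SAP tables:** keep the six-month tables by D01 vaccine. Label Group 3 as *Moderna, with optional Fluzone HD after V02*, give the number who received it, and list late Group 3 events by receipt, marked as descriptive and non-randomised.
4. **Protocol 9.3 and SAP 3.3:** state whether the out-of-design exclusion applies to this dose.

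No separate instruction to confine the Group 1 versus Group 3 description to 21 days is needed, because the objective already does that.

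Cost: one CRF field with a date, one question at a call already scheduled, a table label and a few sentences. The split by receipt is self-selected, so it can only describe.

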2.3.3 Overall Benefit-Risk Conclusion

Considering the measures taken to minimize risk to participants enrolled in this study, the potential risks that may result from study participation are balanced by the anticipated benefits that may be afforded to participants.

3 Objectives and Endpoints

The study objectives and the corresponding endpoints are described in [Table 3.1](#).

Table 3.1: Objectives and endpoints

Objectives	Endpoints
Safety Objective	

To describe the safety profile of Fluzone High-Dose Quadrivalent vaccine and/or Moderna COVID-19 Vaccine administered concomitantly or singly, up to 21 days after injection in each study intervention group.	
Presence of immediate unsolicited systemic adverse events (AEs) reported in the 30 minutes after injectionPresence of solicited (pre-listed in the participant's diary card [DC] and CRF) injection site reactions and systemic reactions occurring up to 7 days after injectionPresence of unsolicited AEs reported up to 21 days after injection

Objectives	Endpoints
	
 Presence of serious adverse events (SAEs) reported up to 6 months after injection Presence of adverse events of special interest (AESIs) reported up to 6 months after injection Presence of medically-attended AEs (MAAEs) reported up to 6 months after injection
Immunogenicity Objectives	
1) To describe the immune response elicited by Fluzone High-Dose Quadrivalent vaccine administered concomitantly or singly, in each study intervention group.	Endpoints for Immunogenicity Objective #1 
 Hemagglutination inhibition (HAI) individual titer on D01 and 21 days after injection of Fluzone High-Dose Quadrivalent vaccine (D22) Individual HAI titers ratio D22/D01 Detectable HAI titer, ie, with a titer ≥ 10 (1/dil) at D01 and 21 days after injection of Fluzone High-Dose Quadrivalent (D22) Seroconversion (titer < 10 [1/dil] at D01 and post-vaccination titer ≥ 40 [1/dil] at D22, or titer ≥ 10 [1/dil] at D01 and a ≥ 4-fold-rise in titer [1/dil] at D22) HAI titer ≥ 40 (1/dil) on D01 and 21 days after injection of Fluzone High-Dose Quadrivalent (D22)
2) To describe the immune response elicited by Moderna COVID-19 Vaccine administered concomitantly or singly, in each study intervention group.	Endpoints for Immunogenicity Objective #2 
 Individual anti-S binding IgG concentration on D01 and 21 days after injection of Moderna COVID-19 Vaccine (D22) Individual anti-S binding IgG concentration ratio D22/D01 2-fold-rise and 4-fold-rise in anti-S binding IgG concentration 21 days post-injection D01

4 Study Design

